## 1 STUDY DETAILS

This is the statistical analysis plan (SAP) for study D5242C00001. The SAP describes the statistical analyses specified in the latest version of the clinical study protocol (CSP) in more detail. Any changes to what is specified in the CSP will be described.

### 1.1 Study Objectives

#### 1.1.1 Co-Primary Objectives

Objective:	Endpoint/Variable:
To evaluate the effect of tezepelumab on:	
Nasal polyp score (NPS)	

• Co-Primary: Change from baseline in total NPS evaluated by nasal endoscopy at Week 52.

Participant reported Nasal Congestion (NC)	

• Co-Primary: Change from baseline in bi-weekly mean Nasal Congestion score (NCS) evaluated as part of the Nasal Polyposis Symptom Diary (NPSD) at Week 52

#### 1.1.2 Key Secondary Objectives

Objective:	Endpoint/Variable
To evaluate the effect of tezepelumab on:	
Loss of smell	

• Change from baseline in bi-weekly mean loss of smell evaluated as part of the NPSD at Week 52.

Nasal polyp-quality of life compared with placebo	

• Change from baseline in SNOT-22 scores at Week 52.

NP surgery and/or receiving systemic corticosteroids (SCS) for NP	

• Time to surgery decision and/or SCS for NP up to Week 52.

• Time to NP surgery decision up to Week 52.

• Time to SCS for NP up to Week 52.

Sinus opacification	

• Change from baseline in Lund Mackay score (LMK) evaluated by computed tomography (CT) at Week 52.

Objective:	Endpoint/Variable
NPSD total symptom score (TSS)	

Change from baseline in bi-weekly mean NPSD TSS at Week 52.

Lung function in participants with co-morbid asthma and aspirin exacerbated respiratory disease (AERD) /nonsteroidal anti-inflammatory drug exacerbated respiratory disease (NSAID-ERD)	

Change from baseline in pre-bronchodilator (BD) FEV1 at Week 52.

### 1.1.3 Other Secondary Objectives

Objective:	Endpoint/Variable
To evaluate the effect of tezepelumab on:	
NPS	

Change from baseline over time in total NPS evaluated by nasal endoscopy through Week 52.

Proportion of participants with (i) <math>\geq 1</math> point reduction and (ii) <math>\geq 2</math> points reduction in NPS at Week 52.

Participant reported NC	

Change from baseline over time in bi-weekly mean NCS evaluated by NPSD through Week 52.

Loss of smell	

Change from baseline in loss of smell evaluated by UPSIT test at Week 52.

Sinus opacification	

Change from baseline in modified LMK score evaluated by CT at Week 52.

Sinus severity score by quantitative CT assessment at Week 52

Systemic corticosteroid use	

Exposure of SCS over 52 Weeks.

NPSD	

Change from baseline by domain of NPSD through Week 52.

Nasal peak inspiratory flow (NPIF)	

Change from baseline in NPIF through Week 52.

Objective:	Endpoint/Variable
Asthma control in participants with co-morbid asthma and AERD/NSAID-ERD	
 
• Change from baseline in ACQ-6 at Week 52.
 

To evaluate the PK and immunogenicity of tezepelumab	
 
• PK: Serum Concentration
 
• Immunogenicity: Anti-drug antibody (ADA)
 

#### 1.1.4 Safety Objectives

Objective:	Endpoint/Variable
To evaluate the safety and tolerability of tezepelumab	
 
• Adverse events (AEs)/serious adverse events (SAEs)
 
• Clinical chemistry/hematology/urinalysis
 
• Vital signs
 
• Electrocardiograms (ECG)
 

#### 1.1.5 Exploratory Objectives

Objective:	Endpoint/Variable
To explore the off-treatment effect and the recurrence rate of nasal polyps after discontinuation of treatment with tezepelumab	
 
• Change from baseline in NPS
 
• Change from baseline in bi-weekly mean NCS
 
• Participants requiring surgery and SCS for NP
 

To explore the effect of tezepelumab on exploratory biomarkers of inflammation and nasal polyposis disease and investigate biomarkers for predicting response to tezepelumab	
Exploratory biomarker parameters:
 
 
• Serum and plasma for protein biomarkers
 
• Whole blood for transcriptomic profiling
 
• Nasal epithelial lining fluid for protein biomarkers
 
• Nasal polyp biopsies for inflammatory cells by histology and immunohistochemistry, and transcriptomic profiling
 

To explore tezepelumab PK in nasal epithelial lining fluid	
 
• Exploratory PK concentrations in nasal epithelial lining fluid
 

Optional exploratory genomics sample	
 
• A blood sample for DNA isolation will be collected from participants who have
 

Objective:	Endpoint/Variable
	consented to participate in the genetic analysis component of the study.
To evaluate the effect of tezepelumab on unplanned health care resource utilization	
 
• Hospitalisations, emergency room, unplanned out participant visits, and urgent care visits.
 

To evaluate the participant reported quality of life outcomes	
 
• Short form 36-item health survey version 2 (SF-36 v2)
 
• European quality of life-5 dimensions-5 levels (EQ-5D-5L)
 
• Work productivity and activity impairment (WPAI)
 

Participant perception of overall symptom severity and change	
 
• Patient Global Impression of Severity (PGI-S)
 
• Patient Global Impression of Change (PGI-C)
 

To evaluate airway inflammation in participants with co-morbid asthma/AERD/NSAID-ERD	
 
• Change from baseline in fractional exhaled nitric oxide (FeNO).
 

Resolution/near complete resolution of nasal polyps (defined as maximum NPS of 1 in each nostril)	
 
• Proportion of participants who achieve a maximum NPS of 1 in each nostril at Week 52.
 

Resolution/near complete resolution of nasal polyps (defined as maximum NPS of 1 in each nostril) and NPSD TSS response	
 
• Proportion of participants who achieve a maximum NPS of 1 in each nostril and NPSD TSS response at Week 52.
 

## 1.2 Study Design

This is a Phase 3, multicenter, randomised, double-blind, placebo-controlled, parallel-group, study to evaluate the efficacy and safety of repeat dosing of tezepelumab 210 mg SC versus placebo in participants with severe chronic rhinosinusitis with nasal polyposis (CRSwNP).

Approximately 400 participants will be randomised globally in a 1:1 ratio to receive tezepelumab 210 mg or matching placebo.

Participants will be stratified by region (China, Japan, and Rest of World [ROW]), prior nasal polyp surgery and co-morbid asthma/AERD/NSAID-ERD. Randomisation will be monitored to ensure that 50%-70% of the study population will have co-morbid asthma/AERD/NSAID-ERD, and at least 50% will have had prior surgery for CRSwNP. When the target percentage of participants in a stratum in a region is reached, consideration will be given to closing the IWRS randomisation for that subgroup, which may be done either overall or within a specific region. Once a subgroup is closed, participants in the screening/run-in period in the closed subgroup will not be allowed to be randomised and will be screen failed.

[figure not shown]
After enrolment, eligible participants will enter a screening/run in period and will have their current inhaled corticosteroid (INCS) therapy standardized to mometasone furoate nasal spray (MFNS) or equivalent INCS at Visit 1 and throughout the screening and study period.

Participants who continue to meet eligibility criteria will be randomised at Visit 3 (Day 0) to receive either placebo or tezepelumab 210 mg SC at randomisation (Week 0) and every 4 weeks thereafter (Weeks 4, 8, 12, 16, 20, 24, 28, 32, 36, 40, 44, 48). A total of 13 doses will be administered. An end of treatment (EOT) Visit will be conducted at Week 52.

The first approximate 200 randomised participants will have a 24-week follow up (FU) period without investigational product (IP) administration to assess durability of benefit. These participants will have the final safety assessment at Week 76. The remaining participants will be followed for 12 weeks after the end of treatment visit, with the final safety assessments at Week 64.

An overview of the study design is provided below in [Figure 1](#).

**Figure 1 Study Design Schema**

Participants who prematurely discontinue IP will be encouraged to remain in the study and undergo appropriate study visits/procedures for the full 52-week planned treatment period, despite no longer receiving treatment. At the IP Discontinuation (IPD) visit the participant will be given the following 3 options (further details are given in the CSP Section 7.1.1):

1. The participant should be encouraged to return for all regular clinic visits and perform all scheduled assessments (excluding IP administration and, in the case of IP discontinuation due to NP surgery, nasal endoscopy and CT) until the EOT visit at Week 52 (+/-5 days).
2. The participant will be offered follow-up on a monthly basis via telephone calls while continuing ePRO data collection on the handheld device at home until the participant completes the EOT visit at Week 52 (+/-5 days). The UPSIT assessment will not be completed at home after IPD visit until the participant returns back to the site at the EOT visit.
3. If the participant cannot or does not wish to comply with any of the options above, (or any component of them such as only telephone-based visits without completion of the eDiary), the Investigator will contact the participant at 52 weeks post-randomisation. No other study assessments will be performed prior to this contact.

### 1.3 Number of Participants

Approximately 400 participants will be randomised to tezepelumab 210 mg Q4W or matching placebo in a 1:1 ratio.

The study is sized to provide compelling statistical evidence for the co-primary endpoints (NPS and NCS) and key secondary endpoints of change from baseline in loss of smell, LMK, and SNOT-22 (considering a significance level of 0.01 in the sample size calculations), as well as sufficient power to assess the composite endpoint of time to SCS and/or surgery (2-sided level of 1%). In addition, this sample size allows assessment of the effect of tezepelumab vs placebo on NPS and NCS in key subgroups and provides a reasonably-sized safety database (CSP Section 9.2).

Assuming a population standard deviation (SD) of 2.25 in total NPS change from baseline and 1.22 in NCS change from baseline, this sample size of 200 participants per arm will provide at least 95% total power to observe a statistically significant difference at a 2-sided 1% level on both co-primary endpoints if the true effect of tezepelumab is -1.8 in total NPS change from baseline and -0.87 in NCS change from baseline. The assumption of true effects is based on reported estimates in the dupilumab Phase III nasal polyp studies. It is expected that treatment with tezepelumab will demonstrate similar or better treatment effects over a 52-week period. The assumed SD was estimated based on the CIs of the corresponding endpoints in the dupilumab Phase III nasal polyp studies ([Bachert et al 2019](#)).

Two hundred participants per arm also provides at least 95% power to detect a statistically significant difference at a 2-sided 1% level in secondary endpoints of change from baseline in loss of smell, LMK, and SNOT-22 (assuming mean [SD] of -1 [1.3], -5 [5.45], and -17.4 [26.8], respectively). The size of the study also provides at least 95% power to detect a statistically significant difference at the 2-sided 1% level in the key secondary endpoint time to SCS and/or surgery for NP, assuming a true reduction in risk of 67% (hazard ratio [HR] of 0.33) with a placebo rate at Week 52 of 35% (placebo data estimated from dupilumab SINUS-52). In addition, this provides at least 80% power to detect a difference (at a nominal 5% significance level) in the key secondary endpoint of time to surgery, assuming a true HR of 0.33 and a placebo rate at Week 52 of 11% (placebo data estimated from pooled dupilumab studies SINUS-24 and SINUS-52). Assuming 50-70% of participants will have co-morbid asthma, the sample size will also provide >80% power for the co-primary endpoints at a 2-sided 5% significance level in the co-morbid asthma subgroups.

## **2 ANALYSIS SETS**

### **2.1 Definition of Analysis Sets**

Participants must have provided their informed consent. If no signed informed consent is collected (major protocol deviation), then the participant will be excluded from all analysis sets defined below. In the case of severe site misconduct or suspected fraud, it may be appropriate to remove sites, participants, or repeated participant information from the reporting of the study. This must be assessed dependent on the individual circumstances, and would be detailed prior to unblinding in a formal file note.

#### Enrolled Analysis Set

This analysis set comprises all enrolled participants who signed the informed consent form, including screening failures, and will be used for the reporting of disposition.

#### Randomised Analysis Set

This analysis set comprises all participants randomised to study treatment, irrespective of whether IP was subsequently taken, and will also be used for the reporting of disposition.

##### **2.1.1 Efficacy Analysis Set**

###### Full Analysis Set (FAS)

This analysis set comprises all participants randomised to study treatment who received at least one dose of IP, irrespective of their protocol adherence and continued participation in the study.

Efficacy analyses will be performed using all participants in the FAS. Participants will be analysed according to their randomised treatment (including in the case of any discrepancies between randomised and actual treatment).

The FAS specifies which participants are included in efficacy analyses. Details of which data are included in efficacy analyses for these participants are given in the respective sections, notably in Section 3.1.3 and Section 4.2.

For consistency with efficacy analyses, demographics and baseline characteristics will be summarised using the FAS.

#### Co-morbid Asthma/AERD/NSAID-ERD Subset

All participants in FAS who have comorbid asthma/AERD/NSAID-ERD at baseline will be included in this subset, irrespective of their protocol adherence and continued participation in the study. Participants will be analysed according to their randomised treatment. ACQ-6, FEV1, and FeNO will be analysed based on the co-morbid asthma/AERD/NSAID-ERD subset.

#### **2.1.2 Safety Set (SS)**

This analysis set comprises all participants who received at least one dose of IP.

Safety analyses will be performed using all participants in the safety analysis set. Participants will be analysed according to their actual treatment in the case of any discrepancies between randomised and actual treatment. Specifically, a participant who has on one or more occasion actually received active (tezepelumab) treatment will be assigned to the tezepelumab group, regardless of the randomised treatment assignment. A participant who has on no occasion actually received any active (tezepelumab) treatment will be assigned to the placebo group, regardless of the randomised treatment assignment.

Safety data will also be listed separately and discussed in the clinical study report (CSR) for any participant who received a treatment that was not the randomised treatment at one or more visits.

Summaries of ADA will also be based on the safety analysis set, using the same approach to handle treatment dispensing errors.

#### **2.1.3 Other Analysis Sets**

##### PK Analysis Set (PKS)

This analysis set comprises all participants in the FAS who received active (tezepelumab) treatment and had at least one detectable tezepelumab serum concentration from a sample

collected post-treatment that is assumed not to be affected by factors such as protocol deviations (PDs) (e.g. disallowed medication or incorrect study medication received). Summaries of PK will be based on the PK analysis set.

#### Additional FU Analysis Set

Additional FU analysis set comprises approximately the first 200 participants who have a 24-week follow-up period post EOT. Only participants who complete Week 64 visit are included in this analysis set, regardless of completion of Week 76 visit or withdrawal from the study after Week 64 visit.

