^c Approximately, the first 200 participants randomised will have a 24-week follow-up period post EOT: V18 (Week 58), V19 (Week 64), V20 (Week 70) and V21 (Week 76). If for any reason a participant in the first set of randomised participants as described, is not willing to participate for a full 24-week FU period and would like to terminate participation in the study, the follow-up discontinuation (FUD) visit should be performed at V19 (Week 64).

^d The remaining, approximately 200 participants randomised will have a 12 -week Follow-up period post EOT: V18 (Week 58) and V19 (Week 64).

^e Unscheduled visits may be initiated as needed, and additional assessments may be performed at these visits as indicated.

^f COVID-19 entry screening questionnaire must be completed for each participant prior to complete study visit activities. Sites should also follow local SARS-CoV-2 testing guidelines outside of CSP study assessments, if applicable.

^g UPSIT smell test will be performed in all countries participating in the study except in countries in which an UPSIT version is unavailable in the applicable native language.

^h The subjects, sites and sponsor will be unblinded to the FENO values prior to randomisation and blinded to the FeNO values post randomisation.

ⁱ Referral for CT scan should be provided at V2 (Week -2) and must be performed after nasal biopsy procedure (if applicable) at V2 only if the participant has met all eligibility criteria at V2. CT should be performed between V2 and V3 after the participant meets the inclusion/exclusion criteria and receive a confirmation from central readers that the inclusion criteria of NPS score is met.

^j The sponsor and site will be blinded to the immunoglobulin, eosinophil, basophil and monocyte counts from the central laboratory reports except screening visits (V1 and V2), any repeat testing that is performed during the screening period prior to Investigational Product (IP) administration at V3.

^k FSH test done only for female participants to confirm postmenopausal status in women < 50 years who have been amenorrhoeic for > 12 month.

^l At dosing visits, PK samples must be collected pre-dose.

- m Neutralising antibody (nAb) testing will be performed for all samples that are ADA positive. Samples that are ADA negative will not be tested for nAb.
- n For IPD, participants should only have nasal epithelial lining fluid collected if the time between randomisation and IPD Visit is \geq 24 weeks.

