should be checked by investigators during the study period. If a participant cannot tolerate MFNS or equivalent INCS during screening period, the participant should be screen failed.

The Principal Investigator should ask participants about SCS (oral and/or, parenteral) use for NP at each visit and record in the eCRF. Participants who require SCS and/or hospitalisation for an asthma exacerbation (see Section 8.2.5.2) or nasal polyp exacerbation during the screening period, should be screen failed and may rescreen once their symptoms improve (see Section 5.4.1).

Participants who experience an asthma exacerbation or worsening of nasal polyposis symptoms during the screening/run-in period (before Visit 2), may extend their screening period to accommodate the time needed for a short course (5-7 days) of systemic corticosteroids (SCS) treatment and return to Visit 2 no sooner than 4 weeks after the last dose of oral corticosteroids. If asthma exacerbation or worsening of nasal polyposis symptoms that require SCS or hospitalisation occurred between Visit 2 and Visit 3 (randomisation), participants should be screened failed and may be rescreened once their conditions are stabilised.

Participants will be provided with an electronic patient reported outcome (ePRO) device to record symptoms throughout the study (see Section 8.1.2). Participants who continue to meet eligibility criteria will be randomised 1:1 at Visit 3 (Day 0) to receive either placebo or tezepelumab 210 mg SC at randomisation (Week 0) and every 4 weeks thereafter (Weeks 4, 8, 12, 16, 20, 24, 28, 32, 36, 40, 44, 48). A total of 13 doses will be administered. An EOT Visit will be conducted at Week 52.

The first approximate 200 randomised participants will have a 24-week follow-up (FU) period without IP administration to assess durability of benefit. These participants will have the final safety assessment at Week 76. The remaining participants will be followed for 12 weeks after the end of treatment visit, with the final safety assessments at Week 64.

If for any reason a participant in the first set of randomised participants, as described above, is not willing to participate for a full 24-week FU period and would like to terminate participation in the study, the follow-up discontinuation (FUD) visit should be performed. The FUD visit should occur at V19 (Week 64).

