8.1.4 Post-randomisation Nasal Polyp Surgery and/or SCS Use

Participants who have a scheduled NP surgery at the time of the study enrolment and randomisation should not be randomised (refer to exclusion criterion 15). After randomisation, surgery should not be planned for the first 3 months unless emergent or deemed necessary by the PI. These cases should be discussed with the AstraZeneca study physician.

Post-randomisation nasal polyposis surgery will, by definition, define a study endpoint. Both the date the decision is made that surgery is warranted (as agreed jointly by both the

participant and the investigator), as well as the date of actual surgery (if available), will be recorded in the eCRF. NP surgery is defined as any procedure involving instruments resulting in an incision and removal of tissue (eg, polypectomy, endoscopic sinus surgery). Post-randomisation surgery procedures performed for NP during the study, including reason for surgery and information whether the surgery was performed as an outpatient or inpatient (ie, including an overnight stay in the hospital) procedure, should be recorded in the Nasal Polyp Surgery eCRF. A nasal endoscopy assessment of NPS (to provide evidence of NP recurrence), a CT scan and PROs should be performed prior to the first (post-randomisation) actual NP surgery. If no such assessment is available, a visit should be scheduled to obtain those assessments. At the time of surgery, participants will be permanently discontinued from IP and assessed as soon as possible per the EOT visit described in the SoA. If surgery is planned during the follow-up period, participants will be assessed by the Investigator and may decide to continue follow-up to the time of surgery or final visit of the study, whichever date comes first.

Rescue treatment of NP or other reasons is defined as requiring treatment with systemic corticosteroids (SCS) for at least 3 consecutive days (a single depo-injectable dose of corticosteroids will be considered equivalent to a 3-day course of systemic corticosteroids). A course of SCS is considered continuous if treatment episodes are separated by less than 7 days. Participants receiving SCS during the study should continue on IP unless the Investigator decides to withdraw the participant from IP due to safety reasons.

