### 3.1.3 Study Periods

The following study periods are defined for analysis purposes:

- **Screening/run-in period:** starting on the date of the first study procedure and ending one day prior to randomisation (for randomised participants) or on the date of the last study procedure (for screening failures). If any participant is re-screened, the latest available screening will be used for this purpose.
- **Planned treatment period:** starting on the date of randomisation (efficacy) and ending on the date of the Week 52 visit or earlier study withdrawal date (for participants not followed up until Week 52). Unless noted otherwise, efficacy analyses will be based on planned treatment period.
- **On-treatment period:** starting on the date of first dose of IP and ending on the earlier (date of last dose of IP + 33 days, date of study withdrawal). Note: The 33 days is derived as dose frequency (28 days) plus 5 days as specified in the CSP Section 1.3.

- **Post-treatment period:** starting on the day after the end of the on-treatment period until the end of the study (Week 76 for the first ~200 participants and Week 64 for the remaining participants) or early withdrawal date.
- **On-study period** (planned treatment and follow-up): starting on the date of randomisation (efficacy) / date of first dose of IP (safety) and ending on the study completion or withdrawal date. For analyses performed at primary database lock, the on-study period is understood to include all data recorded up until the date of the data cut-off for the primary database lock (which includes all follow-up data available at the time of the data cut-off).
- **Additional FU period:** starting on the day after Week 64 visit until the end of the study (Week 76) or early withdrawal date. Only the first ~ 200 participants will continue follow-up beyond Week 64.

If a participant dies, the end dates of the study periods defined above will be capped at the date of death.

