#### **4.2.9 Exploratory Endpoints**

##### **4.2.9.1 Change from baseline in NPS and NCS over time up to Week 76**

To explore the off-treatment effect, change from baseline in NPS and NCS over time up to Week 76 will be analysed using the Additional FU Analysis Set. All the following steps will be performed on Additional FU Analysis Set.

**Step I:** For the data after Week 52 and up to Week 76, set data collected after date of surgery, SCS for NP, or biologic for NP treatment to missing.

**Step II:** Merge the dataset from Step I with each MI dataset from Step 3 in Section 4.2.6.1.

**Step III:** Based on the dataset from Step II, the intermittent missing data after Week 52 and up to Week 76 will be imputed using the MCMC method in SAS PROC MI with an IMPUTE=MONOTONE statement for each treatment group separately. For the NPS, the imputation model will include baseline co-morbid asthma/AERD/NSAID-ERD status, prior surgery status, region, baseline value, all post-baseline timepoints up to Week 76. For the NCS, the imputation model will include baseline co-morbid asthma/AERD/NSAID-ERD status, prior surgery status, region, baseline value, data at Weeks 12, 24, 36, 48, 50, 52, and all timepoints after Week 52 and up to Week 76. Timepoints prior to Week 52 may be further reduced from the model in case of convergence problems. NIMPUTE=1 and MAXITER=5000.

**Step IV:** The remaining monotone missing data will be imputed using the MI procedure with the 'MONOTONE REG' option for each treatment group separately. The same imputation model as in Step III will be used. NIMPUTE=1 and MAXITER=5000.

**Step V:** In the datasets from Step IV, replace post-surgery score with WPS, and replace post-SCS/biologic for NP score with WOCF. If a participant received both NP surgery and SCS for NP/biologic for NP, scores post-surgery will be set to WPS.

The same ANCOVA model described in the primary analyses for the co-primary endpoints in Section 4.2.6.1 (primary estimand) will be used for the timepoints up to Week 76. Descriptive statistics including number of participants, mean, standard error, and LS means will be provided for each timepoint. In addition, the difference in LS means and the corresponding 95% CI will be provided for each timepoint. The LS means and 95% CI over time will be displayed graphically by treatment group.

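### The exploratory off-treatment NPS and NCS curves use only those of the first ~200 participants who complete Week 64, so every point is conditioned on later attendance

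*SAP*

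**What the plan says.** - **Who is meant to be followed.** SAP 1.2 defines the long follow-up group by order of randomisation, to study durability: "The first approximate 200 randomised participants will have a 24-week follow up (FU) period".
- **Who is analysed.** SAP 2.1.3 narrows this for the Additional FU Analysis Set: "Only participants who complete Week 64 visit are included in this analysis set, regardless of completion of Week 76 visit".
- **Where the set is used for efficacy.** SAP 4.2.9.1, on NPS and NCS up to Week 76, states: "All the following steps will be performed on Additional FU Analysis Set". Step I blanks data after surgery, systemic corticosteroids (SCS) or a biologic for polyps. Step II merges the datasets already imputed under 4.2.6.1. Steps III and IV impute intermittent and monotone gaps up to Week 76. Step V then reads: "In the datasets from Step IV, replace post-surgery score with WPS, and replace post-SCS/biologic for NP score with WOCF". Estimates and 95% confidence intervals are planned, without p-values.
- **Where the set is used for safety.** SAP 4.2.10.1 uses it for adverse events in the additional follow-up period, which SAP 3.1.3 defines as "starting on the day after Week 64 visit until the end of the study (Week 76) or early withdrawal date". The SAP amendment history gives adverse-event summaries as the reason for creating the set.
- **What can end follow-up.** Under Protocol 8.1.4, if surgery is planned during follow-up, the participant "may decide to continue follow-up to the time of surgery or final visit of the study, whichever date comes first". Protocol 1.3 (footnote c) and 4.1 ask members of the first group who do not want the full 24 weeks to attend a follow-up discontinuation visit at Week 64.
- **General rule.** SAP 2.1.1 bases efficacy analyses on the full analysis set (FAS), whether or not participants stayed in the study.

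**The concern.** The off-treatment question opens at Week 52, but entry to the analysis is decided twelve weeks later. Anyone in the first group without a completed Week 64 visit is missing from the whole curve, including the on-treatment points. Each estimate therefore describes people selected by a post-randomisation event that lies after most of the points being estimated.

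The objective in SAP 1.1.5 covers the off-treatment effect and recurrence of polyps. Early recurrence is one plausible reason for not reaching Week 64. If so, and if it happens at different rates by arm, both the arm means and the contrast could shift. At stake is how fairly the durability curve represents the group that the protocol set out to follow.

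**Working it through.** The plan states no sample size, power or dropout figure for this analysis, so there is none to reproduce. The check is mainly textual, followed by an illustration.

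**1. Which steps need a Week 64 visit?**
- Step II needs only the 4.2.6.1 datasets, which are complete to Week 52.
- Step III handles intermittent gaps, and Step IV handles monotone gaps such as withdrawal.
- Step V works from event dates and assigns the worst possible score after surgery.

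None of them tests for Week 64 attendance. The restriction comes only from the set definition.

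**2. What observed data are lost?** SAP 3.1.4 sets different schedules after Week 52.
- NCS (Table 3) has 14-day intervals. Those ending before Week 64 are Weeks 54, 56, 58, 60 and 62, so up to five observed bi-weekly means per excluded participant are unused.
- NPS (Table 2) has windows only at Weeks 64 and 76. A participant who leaves before Week 64 normally has no observed off-treatment NPS.

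**3. Who stays in?** Those who attend the discontinuation visit at Week 64 remain. Those lost are participants with no Week 64 visit, which can include someone whose follow-up stopped at surgery between Weeks 52 and 64.

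**4. How large could the effect be?** Let d be the fraction of an arm that is dropped, and Δ how much worse those dropped score than those kept. The full-group arm mean is the completer mean plus d × Δ. Hence

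shift = (completer contrast) − (full-group contrast) = dP × ΔP − dT × ΔT,

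with contrast = tezepelumab minus placebo. A positive shift makes tezepelumab look less effective.

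*Scenario A: surgery only.* Inputs from Protocol 9.2: 11% placebo surgery decisions by Week 52, hazard ratio 0.33, assumed effects −1.8 (NPS) and −0.87 (NCS), NPS SD 2.25. Assumed: constant hazard, the same rates after Week 52, and every case leaving before Week 64.
- Placebo weekly hazard: −ln(0.89)/52 = 0.00224.
- 12-week probability: dP = 1 − exp(−12 × 0.00224) = 0.0265; with the hazard ratio, dT = 0.0088.
- NPS, worst score 8, placebo mean 5 (assumed), tezepelumab 3.2: 0.0265 × 3 − 0.0088 × 4.8 = 0.0796 − 0.0424 = +0.037. At placebo mean 7 it is +0.002.
- NCS, worst score 3, placebo mean 1.5 (assumed), tezepelumab 0.63: 0.0398 − 0.0209 = +0.019. At placebo mean 2.5 it is +0.001.
- Standard error for NPS at 100 per arm: 2.25 × √(2/100) = 0.318, so the largest NPS shift is 0.037/0.318 = 12% of one standard error.

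*Scenario B: other assumed dropout, NPS.*

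| Dropped, tezepelumab / placebo | Δ, tezepelumab / placebo | Shift |
|---|---|---|
| 5% / 5% | 4 / 2 | 0.10 − 0.20 = −0.10 |
| 20% / 20% | 4 / 2 | 0.40 − 0.80 = −0.40 |
| 5% / 10% | 2 / 2 | 0.20 − 0.10 = +0.10 |
| 10% / 20% | 2 / 2 | 0.40 − 0.20 = +0.20 |
| 10% / 10% | 2 / 2 | 0 |

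The sign changes with the assumptions. Scenario A is one assumed case and not a range.

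**The case against.** The strongest defence concerns NPS. With visits only at Weeks 64 and 76, the condition gives almost every analysed participant at least one observed off-treatment score. That stands, so a reader who infers that the condition has no purpose in this analysis goes too far. It holds less well for NCS, where observed diary data are discarded.

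A second defence is that replacing the set with everyone among the first ~200 would bring in people who left before Week 52. Their whole off-treatment course would be imputed under missing at random, for a treatment cessation never observed in them. This also stands, and it is why that population belongs in a sensitivity analysis.

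A reader might infer that participants are removed because they recurred. The documents do not show this. It needs surgery between Weeks 52 and 64, follow-up ending there, and no Week 64 visit. The Protocol 8.1.4 wording is permissive, and nothing tells a surgical participant to skip the Week 64 discontinuation visit. Nor can one conclude that surgical recurrence goes uncounted: the SAP amendment history moves surgery and SCS to Week 76 into a separate exploratory plan that is not available here.

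Scenario A also has weak inputs. It uses a surgery-decision rate as a surgery rate, carries an on-treatment hazard ratio into the off-treatment period, and ignores other withdrawals.

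**Conclusion.** The point holds as a modest improvement to an exploratory analysis. A set suited to adverse events after Week 64 is reused for an efficacy curve whose off-treatment part starts at Week 52. This conditions every point on later attendance, discards collected NCS data, and can drop a surgical case that Step V is written to score.

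Neither the size nor the direction of any bias can be determined, because the documents give no dropout rates after Week 52. The number affected may be small, given the Week 64 discontinuation visit. A claim that the set favours tezepelumab is not supported: the illustrations go both ways. Nor does the point reach the co-primary or key secondary results at Week 52, which use other sets and lie within a testing hierarchy that this analysis is outside.

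**What to change.** In SAP 4.2.9.1:
- Make the main set the FAS participants among the first ~200 randomised who entered follow-up after Week 52, without the Week 64 condition, and apply Steps I–V. State how entry is determined. This is still a post-randomisation condition, but it precedes the off-treatment period.
- Report by arm and reason how many lack a Week 64 visit.
- Keep the Week 64 completer set for the additional follow-up adverse-event summaries, and as a sensitivity analysis here.
- Optionally add a further sensitivity analysis in all FAS participants among the first ~200, including those who left before Week 52.

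The cost is SAP wording and an additional imputation run. More values are imputed under missing at random, notably for NPS. Convergence may be harder: the SAP amendment history already mentions the risk, and Step III allows earlier time points to be removed from the model. SAP 2.1.4 rules out SAP updates after the primary database lock. If that has passed, the analysis can be added in the clinical study report as a stated deviation, as Protocol 9.4 provides.
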